# 13.2 Justification for exclusion of children

Children less than 18 years old are excluded from the trial. Because ME/CFS is rare in children, pediatric cases may not be representative of the typical pathophysiology of the condition.

# *13.3* Justification for exclusion of pregnant women

Pregnancy-related physiological changes and fatigue would impact the interpretability of the results. Also, pregnancy is a contraindication for MRI. For these reasons, pregnant women are excluded from the study.

# *13.4* Justification for exclusion of women who have given birth in the past year

Post-partum fatigue is likely to confound the results of the study.

# *13.5* Justification for exclusion of those who lack consent capacity

Persons who lack consent capacity will be excluded from this study. This study provides no direct benefit to the participant, involves varied and complex testing, and is more than minimal risk.

Cognitive impairment severe enough to affect consent capacity would be unexpected in our target population. Such patients also would be unable to properly perform several study procedures, in particular patient-reported outcome scales and neurocognitive testing. For these reasons, persons with severe cognitive impairment will be excluded. If necessary, a CC-credentialed LIP will assess if a person is too cognitively impaired to participate in the protocol. While unexpected, a consultation to assess consent capacity will be obtained from the NIH Ability to Consent Assessment Team [contact]) if necessary.

#### *13.6* Justification of exclusion of non-English speakers

Persons who are not fluent in the English language will be excluded. Such persons would be unable to properly perform several study procedures that are only valid in the English language, in particular patient-reported outcome scales and neurocognitive testing.

### *13.7* Justification for inclusion of employees

NIH staff will not be solicited for participation, but will not be excluded if they express the desire to enroll. Protections for employees and staff participating in this study include 1) assuring that the participation or refusal to participate will have no effect, either beneficial or adverse, on the subject's employment or position at NIH, 2) giving employees and staff who are interested in participating the "NIH Information Sheet on Employee Research Participation" prior to obtaining consent, and 3) assuring that there will be no direct solicitation of employees or staff. If the individual obtaining consent is a co-worker, an independent person (either from Bioethics or NIMH Human Subjects Protections Unit) will monitor the consent process for any NIH employees that desire to participate. Employees that participate in this protocol during work hours will be informed that they must obtain their supervisor's permission and that per NIH guidelines they will not be paid.

# *13.8* Justification for sensitive procedures

Drug tapering is a sensitive procedure that may be performed on a subset of patients. Allowing for the use of central-acting medications would create problematic heterogeneity in the study groups. The impact of central-acting medications on biological measurements, in particular those made in blood, cerebrospinal fluid, fMRI, and neurocognitive testing, are also significant. As these medications do not treat the underlying cause of ME/CFS, do not substantially reduce morbidity or mortality, and have not been shown to lead to substantial clinical improvements, the period of tapering withdrawal will not likely to have substantial impact on health outcomes. As it is anticipated that a majority of participants will be taking at least one of these medications, it is necessary to allow for medication withdrawal rather than automatically excluding the potential participants. Participants taking stable doses of medications for medical diseases or psychiatric diagnoses will not be withdrawn from their medications. All withdrawal plans will require the agreement and full cooperation of the participant's primary care physician. If psychiatric medications prescribed by the participant's psychiatrist are being withdrawn, agreement and full cooperation from the psychiatrist will also be obtained. Participants unable to tolerate drug tapering always have the option to remain or restart their medications and withdraw from the study.

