# 3.3.3 Additional exclusion criteria for participants with PI-ME/CFS for exercise stress visit

1. Current (within 1 week) use of prescription or over-the-counter medications, herbal supplements, or nutraceuticals that may influence brain excitability that the potential participant is either unwilling or clinically unable to safely wean off for the duration of the period of the exercise stress visit. The possibility for a potential participant to be weaned off medication will be cooperatively determined by both the clinical investigative team and personal physicians. Examples of medications that influence brain excitability include tricyclic antidepressants, hypnotic, antiepileptic, antipsychotic medication, stimulants, antihistamines, muscle relaxants, dopaminergic medications, and sleep medications.

3.3.4 Additional exclusion criteria for healthy volunteer group

- 1. Substantial daily fatigue as determined using PROMIS-SF Fatigue: score of > 17.
- 2. Significant neurological disorder (e.g. neurodegenerative disorder, stroke, epilepsy).
- 3. Current (within 1 week) use of prescription or over-the-counter medications, herbal supplements, or nutraceuticals that may influence brain excitability

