#### 4.5 Phenotyping Visit (Visit 1: Phenotyping)

The phenotyping visit will take place at the NIH Clinical Center up to 12 months before the exercise stress visit and is expected to last 5 days for HV and COVID-19 HV participants and 10 days for PI-ME/CFS participants. Phenotyping may occur on either an outpatient or an inpatient admission basis, depending on convenience. Information collected during the phenotyping visit will be used to determine PI-ME/CFS case status as well as to determine eligibility for the exercise stress visit. All procedures are for research purposes.

Consent will be obtained before any study procedures, including screening procedures, are done. Eligibility criteria will be reviewed during the consent process. An eligibility criteria checklist will be reviewed on Visit 1 completion and documented in the protocol's research records.

CNS IRB Protocol Template (2.5.15)

During the phenotyping visit, clinical information that is collected may impact participant eligibility. All participants in the PI-ME/CFS group will have documentation of being diagnosed with the illness in the community. In this way, PI-ME/CFS participants found not to meet inclusion/exclusion criteria during the phenotyping visit still represents what ME/CFS is in the community. For this reason, PI-ME/CFS participants that are found to have alterative or concomitant diagnoses that would otherwise exclude from study participation may still be invited to complete all of the phenotype visit procedures.

Participants in the HV and COVID-19 HV groups may be found to meet exclusion criteria during Visit 1. Such participants are also permitted to complete Visit 1 procedures, as long as they do not have substantial daily fatigue nor concerns for safety. Samples and data from these participants will be used in the primary analysis. HV and COVID-19 HV participants found to have substantial daily fatigue will have their study participation ended immediately and will not be used in primary analyses. Study participation for HV individuals meeting exclusion criteria will be complete at the end of Visit 1. Study participation for all COVID-19 HV individuals will be complete at the end of Visit 1.

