- Cytapheresis (Option A): Participants choosing cytapheresis will undergo apheresis to collect of immune cells for immunology testing. Cytapheresis takes about 2.5 hours
- Immune cell blood collection (Option B): For participants unwilling or unable to undergo cytapheresis, a blood draw will be performed instead. Up to 100mL of blood will be drawn for the storage of serum, plasma, and PBMCs. Blood draws take about 30 minutes. Typically, no more than 150ml of blood will be drawn in a single day. No more than 550ml of blood will be drawn over an 8-week period, per NIH guidelines.

Participants may be asked to undergo immune cell collection procedures an additional time during the period of their study participation.

4.5.21 : Medication Review and Wash-out Planning (ME/CFS only): Medications that may interfere with measures of brain excitability have the potential to confound several of the proposed study results. Examples of such medications include tricyclic antidepressants, hypnotic, antiepileptic, antipsychotic medication, stimulants, antihistamines, muscle relaxants, dopaminergic medications, opiates, and sleep medications. In clinical practice, participants with PI-ME/CFS often take large numbers of medications for their disorders, including those that might impact brain excitability. However, there are currently no medications that have been demonstrated to effectively treat PI-ME/CFS, and many of the medications these patients take have a negligible impact on the symptom of their illness. Therefore, to increase study homogeneity and reduce potential confounding from medications, a medication review will be conducted and a medication wash-out plan determined for its participants prior to participation in the exercise stress visit or the optional fMRI and TMS procedures.

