## **12** Statistical Analysis

# 12.1 Analysis of data/ study outcomes

The studies performed under this protocol are exploratory. Quantitative research data will be acquired and logged into a database. The PI or designated investigator will monitor data integrity. Because a variety of types of data will be obtained in the study, the statistical methods most appropriate for the nature of the data will be used. Some of the relevant statistical approaches are as follows:

We are primarily interested in evaluating whether various types of data obtained are significantly different between the three groups as measured in cross-section during the phenotyping visit as well as between HV and PI-ME/CFS groups before and after an exercise stress. Each of these groups will be characterized using standard descriptive statistical methods.

As noted in Section 4.5, ME/CFS participants that are found no to meet the strict inclusion/exclusion of this study all have been diagnosed with ME/CFS by health providers and represent ME/CFS in the community. HVs and COVID-19 HVs that do not have fatigue or PEM may also be found to medical issues or other findings that would exclude them from meeting the strict inclusion/exclusion criteria of being healthy, but still represent a non-fatigue comparator to ME/CFS patients. The primary focus of the analyses detailed below will be between adjudicated ME/CFS participants and HVs and COVID-19 HVs that meet all inclusion/exclusion criteria. If the result of a primary analysis is positive, a secondary analysis will be repeated using all of participants. Findings that remain robust even when less stringent inclusion/exclusion criteria are used suggest that they are more likely to be replicable in community cohorts and perhaps worthy of further exploration.

For each continuous-scale outcome, repeated measures analysis of variance (ANOVA) will be used to test whether there are significant differences in cross-sectional measurements as well as in the pre and post measurements among two groups by using F tests. These initial tests will be performed using the adjudicated PI-ME/CFS group (i.e. participants determined to have PI-ME/CFS by the protocol's adjudication process) compared to HV and COVID-19 HV participants meeting all inclusion and exclusion criteria. The cross-sectional analyses may then be repeated using all HV and COVID-19 HV participants that did not report substantial clinical fatigue as noted above.

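### Visit 1 compares patients who may still be taking brain-excitability drugs with controls required to be off them, and Section 12.1 has no step that checks Visit 1 findings for a drug effect

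*Combined protocol and SAP*

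**What the plan says.** **Controls.** Sections 3.3.4 (HV) and 3.3.5 (COVID-19 HV) exclude a control for "Current (within 1 week) use of prescription or over-the-counter medications, herbal supplements, or nutraceuticals that may influence brain excitability".

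**Patients.** The phenotyping exclusions for PI-ME/CFS (Section 3.3.2) contain no drug item. The patient drug rule in Section 3.3.3 applies to the exercise stress visit only, and only to those who will not or cannot wean. Section 4.5.21 provides for "a medication wash-out plan determined for its participants prior to participation in the exercise stress visit or the optional fMRI and TMS procedures". The schedule of events places wash-out monitoring between visits and at Visit 2.

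**The sponsor's view of these drugs.** Section 4.5.21: "Medications that may interfere with measures of brain excitability have the potential to confound several of the proposed study results". Section 13.8: "The impact of central-acting medications on biological measurements, in particular those made in blood, cerebrospinal fluid, fMRI, and neurocognitive testing, are also significant". On expected use, Section 13.8 says: "As it is anticipated that a majority of participants will be taking at least one of these medications".

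**Analysis.** Section 12.1 asks whether data are "significantly different between the three groups as measured in cross-section during the phenotyping visit as well as between HV and PI-ME/CFS groups", the latter on either side of the exercise test. It adds: "The primary focus of the analyses detailed below will be between adjudicated ME/CFS participants and HVs and COVID-19 HVs that meet all inclusion/exclusion criteria". Positive results are then repeated with looser eligibility, and a result that survives is read as more likely to replicate in the community. Section 12.1 also plans univariate ANOVA on the pre-exercise and post-exercise measurements separately. The only covariates it names are in the imaging models (group, behavior, fatigue scores).

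**Protected measures.** Optional fMRI and TMS follow wash-out where it is required (Sections 5.1.7, 5.1.8). Autonomic testing is not done on interfering drugs (Section 4.5.19).

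**The concern.** Blood, CSF, neurocognitive tests, Holter and the effort task (EEfRT) are collected from patients at Visit 1 before any wash-out. Adjudication follows Visit 1, so it cannot change the state in which those samples were taken. Fully eligible controls are off the same drugs. The group contrast is then disease plus medication against neither.

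The protocol accepts a taper that it rates as more than minimal risk (Section 9.24) because it regards these drugs as a source of confounding. Yet the mandatory Visit 1 measures do not benefit from that taper. A drug difference could pass into the list of hypotheses, the choice of markers for ROC analysis, and the effect sizes for the larger study. A multiple-comparison correction lowers the rate of false positives but leaves the bias in the estimate.

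**Working it through.** **1. Inputs.** From the documents: 20 completers per group (Section 12.2), alpha 0.05 (Section 12.1, taken as two-sided), and a majority of patients medicated (Section 13.8). There is no stated figure to reproduce, because the documents give no drug effect, direction or exact share. Assumed: share medicated p = 0.51 to 0.60 and drug effect d = 0.3 to 0.8 SD.

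**2. Bias with no disease effect and drug-free controls.** Bias = p × d. At the low end 0.51 × 0.3 = 0.15 SD, and at the high end 0.60 × 0.8 = 0.48 SD.

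**3. Rejection rate of a patient-versus-control t test.** Simulated with 60,000 replicates and three groups of 20. The last column requires a significant three-group F test (standing in for the overall multivariate test of Section 12.1) and then p < 0.025 pairwise.

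| p | d (SD) | Bias (SD) | All one way | A quarter opposite | Half opposite | All one way, 10% of controls medicated | F test first, then 0.025 |
|---|---|---|---|---|---|---|---|
| 0.51 | 0.3 | 0.15 | 7.5% | 5.6% | 4.9% | 6.5% | 3.3% |
| 0.51 | 0.5 | 0.26 | 12.3% | 6.5% | 5.2% | 9.5% | 6.1% |
| 0.60 | 0.5 | 0.30 | 14.9% | 7.3% | 5.0% | 11.6% | 8.0% |
| 0.60 | 0.8 | 0.48 | 29.6% | 10.6% | 5.1% | 21.5% | 18.7% |

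With no drug effect the rates are 5.0% (single test) and 1.9% (last column).

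**4. What the existing plan covers.**

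| Visit 1 measure | Repeated before exercise at Visit 2? |
|---|---|
| Blood | Yes (4.6.14) |
| TOVA, HVLT-R, BVMT-R, and the B Test and/or Dot Test | Yes (4.6.15) |
| Holter | Yes (4.6.16) |
| EEfRT | Yes (exercise stress visit table, 25.1) |
| Other neurocognitive tests | No |
| CSF | No; the Visit 2 LP is on post-exercise day 3 (4.6.19) |
| Any contrast with COVID-19 HV | No; that group has no Visit 2 (3.1) |

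**5. Precision of an off-drug subset.** At 60% medicated, 20 × 0.4 = 8 patients remain. The 95% CI half-width is t(0.975) × √(1/n1 + 1/n2). For 20 v 20 this is 2.02 × √0.100 = 0.64 SD, and for 8 v 20 it is 2.06 × √0.175 = 0.86 SD. Power for a 0.8 SD difference falls from 69% to 45%.

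**6. What the subset cannot show.** Suppose the estimate falls from 0.80 SD in all patients to 0.50 SD off drug. A 0.5 SD drug effect in 60% gives 0.50 + 0.6 × 0.5 = 0.80. No drug effect, with medicated patients sicker at 1.0 and the others at 0.5, gives 0.6 × 1.0 + 0.4 × 0.5 = 0.80. The two explanations fit equally well.

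**The case against.** **A washed-out comparison is already planned.** A reader might infer that Section 12.1 contains no contrast free of the imbalance. That is not so: its pre-exercise ANOVA compares HV with patients mostly after wash-out. This stands and narrows the point. What is missing is any link from that result back to Visit 1 findings, and cover for the measures marked No above.

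**The size is assumed.** This stands. The drugs listed in Section 4.5.21 include stimulants as well as hypnotics and antipsychotics, so effects need not run one way. The expected majority is also not a figure for the adjudicated set. At an assumed 30% medicated, the rejection rate is 6–11%. However, willingness to wean for Visit 2 does not make a patient drug-free at Visit 1.

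**The repeat analyses.** A reader might infer that these let drug artefacts through preferentially. The documents do not support that, because the added controls are those who fail some criterion and listed-drug use is one such criterion. With 10 added controls (assumed), the share of first positives that stay significant is 56–60% if half of the 10 are medicated and 31–47% if all are, against about 61% with no drug effect. All that can be said is that the repeats are defined by eligibility and so are not a test of medication.

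**The study is exploratory.** Section 12.1 lists only some of its methods, so adjustment is unplanned, not excluded. That limits severity. It does not remove bias from effect sizes carried into a larger study.

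**Conclusion.** The point holds for the mandatory Visit 1 measures, and the remedy is cheap. The eligibility imbalance is in the text, the sponsor itself calls the drug effects significant for blood, CSF and neurocognition, and no step in Section 12.1 tests whether a Visit 1 difference reflects medication. It does not hold for optional fMRI, TMS or autonomic testing.

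The magnitude is unknown. About 7.5–30% rejection, with bias of 0.15–0.48 SD, rests on 20 per group, 51–60% medicated, effects of 0.3–0.8 SD all in one direction, drug-free controls and no disease effect. It falls to about 5% if effects run equally in both directions. A reader might infer that Visit 1 differences will be drug artefacts. The documents show only that the two explanations are not told apart.

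Nor can all analyzed controls be taken as drug-free. For controls found at Visit 1 to meet an exclusion criterion but without substantial fatigue or safety concerns, Section 4.5 says "Samples and data from these participants will be used in the primary analysis", whereas Section 12.1 puts its primary focus on those meeting all criteria.

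**What to change.** In Section 12.1:

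1. Tabulate listed-drug use by group at Visit 1, including any control kept despite meeting an exclusion. For each positive Visit 1 comparison, report the estimate and 95% CI in PI-ME/CFS participants not on listed drugs beside the main result. Treat this as a caveat, not as a condition that the finding must pass. State that the subset is small and may be milder, since many of these drugs are taken for symptoms.
2. Where the measure is repeated before exercise at Visit 2, report the already planned PI-ME/CFS v HV result beside the Visit 1 finding, noting that some stable drugs may continue (Section 4.5.21).
3. Label Visit 1 findings with no such repeat (COVID-19 HV contrasts, CSF, the other neurocognitive tests) as not separated from medication.

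A medication covariate is not proposed. Eligible controls are all off drug, so its coefficient could be estimated only within the patient group.

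**Cost.** SAP wording and a few extra analyses. Patient drug use is already recorded at the Visit 1 medication review, and applying Sections 3.3.4 and 3.3.5 already requires asking controls. The price is wide intervals in the subset and an answer that cannot separate drug effect from severity.

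**To reconcile separately, with no clinical rule proposed here.** (a) Sections 4.5 and 12.1, on controls who meet an exclusion. (b) The statements in Sections 4.5.21 and 13.8 that stable drugs for medical or psychiatric diagnoses are not withdrawn, against Section 3.3.3 and the later statement in 4.5.21 that exclude patients who cannot come off their drugs.

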The nature of the medication taper will depend on the particularities of the medication. Some medications will be able to be stopped immediately. Other medications may require a tapering regimen over days to weeks. The longest taper anticipated will be with the SSRI/SNRI class of medications which can require up to 6 weeks to taper. The timing of the medication withdrawal will depend on the length of time required to successfully withdraw a medication, the number of medications that require withdrawal, and the anticipated time for the inpatient visit. In the case of participants taking multiple medications, withdrawal will likely be sequential. The goal is for participants to be off of potentially interfering medications for at least 5 plasma half-lives prior to their inpatient visit.

Participants will be monitored at a minimum of weekly per telephone during outpatient withdrawal period by a clinically-credentialed member of the study staff. An AE baseline assessment will be performed per phone at the time of beginning of tapering, at least once during the tapering period, and at least once during the period off study drug prior to admission. Closer monitoring may occur at the initiation of the withdrawal or if the participant develops withdrawal issues. Participants with severe withdrawal-related AEs will receive appropriate care from their involved physicians, which may include hospitalization and/or restarting the medication. Participants unable to withdraw off medications will be excluded from the study. After completion of the exercise stress visit, participants may be titrated back onto their baseline type and level of medication in conjunction with the care of their physician care providers.

4.5.22 : Sedation during LP (optional): Sedation with low-dose benzodiazepines may be used for participants with anxiety during the LP. All participants receiving sedation during the study will be monitored for side effects.

4.5.23 : Fluoroscopic-guided LP (optional): If the study investigators determine that the LP should be done under fluoroscopy because of a participant's body habitus, the procedure will be done in Radiology at the Clinical Center. The fluoroscopic-guided LP involves exposure to radiation. The radiation exposure is not required for medical care and is for research purposes only.

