## 9.24 Risks of medication washout

There is a more than minimal risk for the planned tapering off of medications that potentially interfere with brain excitability. Participants may experience an increase in

their typical symptoms or experience symptoms related to the cessation of medications. Patients may decide to discontinue with the medication taper if it is too difficult for them to tolerate.

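### Only PI-ME/CFS patients are withdrawn from centrally acting drugs before Visit 2, and the planned Visit 2 comparisons with healthy volunteers contain no check for withdrawal effects

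*Combined protocol and SAP*

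**What the plan says.** **Who is withdrawn.** Section 4.5.21 restricts medication review and wash-out to ME/CFS participants. Under Section 3.3.3 a patient on a drug that may influence brain excitability is excluded from Visit 2 if "either unwilling or clinically unable to safely wean off for the duration of the period of the exercise stress visit". For HV, Section 3.3.4 lists "Current (within 1 week) use of prescription or over-the-counter medications, herbal supplements, or nutraceuticals that may influence brain excitability" as an exclusion and offers no option to wean. Section 4.5 ends participation after Visit 1 for HV who meet an exclusion. Only PI-ME/CFS and HV participants attend Visit 2 (Section 4.1).

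**How many.** Section 13.8 gives no figure. It says "As it is anticipated that a majority of participants will be taking at least one of these medications", but also "Drug tapering is a sensitive procedure that may be performed on a subset of patients" and "Participants taking stable doses of medications for medical diseases or psychiatric diagnoses will not be withdrawn from their medications".

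**How long off drug.** Section 4.5.21 states: "The goal is for participants to be off of potentially interfering medications for at least 5 plasma half-lives prior to their inpatient visit". Section 4.5.12 adds that withdrawal is finished before home activity monitoring, which lasts at least five days before admission.

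**What stopping may do.** Section 9.24 says participants may have an increase in "their typical symptoms or experience symptoms related to the cessation of medications".

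**What is analysed.** Section 12.1 names comparisons "between HV and PI-ME/CFS groups before and after an exercise stress". It uses repeated measures ANOVA, univariate ANOVA at each time and on change, and fMRI regressions whose predictors are group, fatigue scores and task behaviour. None of these uses medication or wash-out status.

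**The concern.** The taper is there to stop drugs confounding the Visit 2 measurements. It may bring in a second confounder, recent withdrawal, which by design can occur in one group only. Fatigue, sleep, cognition and brain activity are Visit 2 outcomes, and all could plausibly be affected by stopping a hypnotic, stimulant or antidepressant. If such an effect is present, the group term in Section 12.1 absorbs it.

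The study is exploratory, but Sections 4.1 and 12.2 say its results will generate hypotheses and supply effect sizes for a larger study. A withdrawal artefact could therefore be carried forward as a feature of the disease. Section 12.3 says an interim analysis of the ME/CFS and HV cohorts has already begun, so the check needs to be specified soon.

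**Working it through.** **1. The plan's own figures.** There is none on this point. Section 12.2 cites 12 subjects for 80% power at 0.05 in single-voxel imaging, without an effect size or SD, so it cannot be reproduced. The only figure used here is its 20 participants per group.

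**2. Exposure by group at Visit 2.**

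| | PI-ME/CFS | HV |
|---|---|---|
| On a listed drug at entry | Taper or exclusion (3.3.3); stable doses for a diagnosis not withdrawn (4.5.21, 13.8) | Excluded (3.3.4) |
| Planned withdrawal | Yes, in an unstated share | None |
| Term in the 12.1 models | None | None |

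**3. Bias in a comparison of levels.** Let p be the share of patients tapered and w the withdrawal effect in SD units. With no HV tapered, the spurious difference is p × w. Both values are assumptions. The rejection rate uses a two-sided two-sample t test at 0.05 with no true disease effect and noncentrality (p × w)/√(2/20).

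| p | w (SD) | p × w (SD) | Rejection, 20 v 20 |
|---|---|---|---|
| 25% | 0.25 | 0.0625 | 5.4% |
| 60% | 0.25 | 0.15 | 7.5% |
| 60% | 0.5 | 0.30 | 15.2% |

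Simulating a mixed patient group instead of a uniform shift gives slightly lower rates (5.3%, 7.4% and 14.5%), because mixing adds variance. More participants do not help: with 28 of 50 tapered and w = 0.5, the bias is 0.28 SD and about 27% of tests reject at 50 v 50.

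**4. Pre-to-post change.** If withdrawal adds a constant w to a patient's values throughout the stay, then (post + w) − (pre + w) = post − pre, and it cancels. It does not cancel if it fades during the stay or alters the response to exercise.

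**5. Time off drug.** Five half-lives leave 0.5⁵ = 3.1% of the drug. That deals with residual drug. Neither this goal nor the monitoring period shows that withdrawal symptoms have resolved.

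**6. Fatigue as a covariate.** Adjusting the fMRI models for fatigue does not separate the two explanations, because fatigue can come from either.

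**7. What strata can show.** Suppose 8 or 12 of the 20 patients were never on a listed drug. The 95% half-width against 20 HV is t × √(1/n + 1/20):
- n = 8: 2.056 × 0.418 = 0.86 SD
- n = 12: 2.042 × 0.365 = 0.75 SD
- all 20 patients: 2.024 × 0.316 = 0.64 SD

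For an assumed true difference of 0.8 SD, power is about 45% with 8 patients and 56% with 12. A stratum test can therefore miss a real effect about half the time.

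**The case against.** The case on the other side is substantial.

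- **Exposure may be modest.** A reader might infer that most Visit 2 patients have been withdrawn. The documents do not say so: a majority is expected to be taking such a drug, while tapering is for a subset. Section 4.5.21 excludes patients whose withdrawal would be high-risk and those who cannot withdraw, so the hardest cases should not reach Visit 2. It also says many of these drugs have little effect on symptoms, and its wash-out targets include as-needed and sub-therapeutic use. This stands, and the tapered share is unknown.
- **Drug clearance is not the only timing rule.** Withdrawal must also be finished before home monitoring, with telephone contact at least weekly during the taper. This stands, though neither rule requires symptoms to have settled.
- **Much of the study is protected.** Visit 1 comparisons precede the wash-out, apart from optional fMRI and TMS, and a constant effect cancels in change scores. This stands and limits the point.
- **Multiplicity correction is planned.** It lowers the error rate of each test but does not remove the shift in the group difference.
- **The plan is exploratory and leaves methods open.** Section 12.1 would permit a wash-out analysis, but it does not plan one. The study's purpose makes a descriptive check sufficient; it does not make the check unnecessary.
- **Some worsening may be unmasked disease.** An increase in usual symptoms off drug may be what the taper is meant to reveal. That is fair, and it is a reason to report the strata without a rule that discards findings.

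**Conclusion.** The point holds for Visit 2 comparisons of levels between PI-ME/CFS and HV: pre-exercise, post-exercise, fMRI, sleep EEG and symptoms. Planned withdrawal is confined to one group, the protocol accepts that it can have effects, and the analysis has no means of showing them. Change from pre- to post-exercise is exposed only if the effect evolves during the stay or interacts with exercise.

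The size is not known. Under the assumptions shown, false-positive rates run from close to nominal (5.4%) to about 15%. Reading 15% as the expected rate would be wrong: it takes the upper end of two assumed inputs and describes a single uncorrected test. The documents likewise do not support a claim that any particular Visit 2 result is due to withdrawal. This is an inexpensive improvement that should be made; it does not invalidate the design.

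**What to change.** In Section 12.1:

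1. Code each Visit 2 patient as not on a listed drug, tapered, or still on a listed drug. Record the last-dose date for each withdrawn drug. Section 4.5.21 describes plans and calls but does not say these dates are captured, so for completed patients they may have to be retrieved.
2. Reconcile Section 3.3.3 with Sections 4.5.21 and 13.8, which together decide whether the third category can occur. No view is taken on which is right, and no change to the taper is proposed.
3. For each positive Visit 2 finding, show estimates with 95% intervals for each patient stratum v HV and for tapered v not-tapered patients.
4. For measures taken at both visits (questionnaires, neurocognitive tests, the effort-for-rewards task), compare the change from Visit 1 to Visit 2 pre-exercise between tapered patients, non-tapered patients and HV. This change mixes loss of drug effect with withdrawal and can span up to 12 months, so the non-tapered and HV changes are needed as the reference.
5. Where an effect is concentrated in tapered patients, report that withdrawal cannot be excluded as an explanation. Do not use a non-significant stratum to reject a finding.

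The cost is some plan wording, one extra table per finding and the collection of last-dose dates. The drawback is strata of perhaps 8 to 12 patients, which may also differ in severity. This is a descriptive check and not a powered test.
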